### Sub-Group Analysis

We will repeat our analyses of individual- and area-level outcomes for the following subgroups:

• Small versus larger SL schemes. We propose this partly because the larger schemes have been politically contentious (following the change of government in 2024, changes were announced to make it easier for LAs to set up large schemes without needing national government permission), and partly because we hypothesise that resident displacement occurs less in larger schemes – particularly where the schemes extend across the whole local authority area. For this purpose, we will define larger schemes as those covering 90%+ of the Local Authority population (Census 2011): 2012\_Newham, 2014\_BarkingandDagenham,

2015\_Croydon, 2015\_Liverpool, 2015\_WalthamForest. Small schemes will in this analysis be defined as those covering up to 20% of the population. Schemes of intermediate sizes will be ignored in this analysis.

London versus outside London. Comparisons with London are useful because it has a unique housing market and some of its areas were settings for the Olympic Games (a potential confounder).

To examine impacts on equity, we will run the following area-level subgroup analyses by ranking local authorities:

- **Level of deprivation**: lower half (least deprived), upper half (most deprived)
- Proportion of population from a Non-White ethnic background: lower half (low proportion), upper half (high proportion)
- **Proportion of population under 16**: lower half (low proportion), upper half (high proportion)
- Proportion of population over 75: lower half (low proportion), upper half (high proportion)

APS includes items that are relevant to the following equity dimensions covered in the PROGRESS+ framework: Place of residence (which we operationalise as region); Ethnicity, Occupation, Gender, Religion, Education as well as participants who live on their own and participants with child dependents. Occupational status and education can be considered proxies for socio-economic status. Furthermore, the survey asks about long term and limiting health conditions, allowing us to consider these dimensions of disability. It also asks about cohabiting same sex partners. We will incorporate these dimensions into the equity analysis where sample sizes allow us to do so.

To address potential multiple testing issues with the secondary analyses, will adjust the significance tests according to a Benjamini-Hochberg False Discovery Rate of 5% [58].

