In this setting with staggered intervention timing the OLS estimator of β in the canonical two-way fixed effects regression yields an unbiased estimate of the treatment effect only if there is no treatment effect heterogeneity, i.e. if all LSOAs have the same treatment effect and if the treatment has the same effect regardless of how long it has been since the treatment started. The bias occurs because the OLS estimator is a weighted average of comparisons between treated and not-yet-treated units as well as between treated and already-treated units. If, for example, the treatment effect gets stronger over time, the parallel trends assumption discussed above does not hold for the latter comparison [3,4].

The recent literature on difference-in-differences has proposed alternative estimators that overcome the problem of the "forbidden" comparison between treated and already-treated units by making transparent exactly which units are being used as comparison [5]. We will apply the Callaway and Sant'Anna estimator as our main method [6]. This estimator allows for arbitrary treatment effect heterogeneity and dynamic effects by deconstructing the estimation of the overall treatment effect into estimation of so-called group-time average treatment effects. We will apply different aggregation schemes to explore the overall effect as well as treatment effect heterogeneity over time and across groups.

To assess the plausibility of the parallel trends assumption, we will examine the trends in the outcome measures for the treatment and control units in the before period by plotting the raw data over calendar time for the treatment and control units, with the treatment units and their matched control units. We will test if the estimated treatment effects for the three years before the intervention are jointly statistically significantly different from zero. Recent reviews discuss the difficulties with formally testing parallel trends as the analysis may be underpowered [5,7]. Analysts are advised to also assess event time plots and to exercise a degree of pragmatism in cases of small deviations from no-effect before the intervention.

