We will apply non-linear DID models [31] such as Poisson models for counts or, alternatively, using logit models and dichotomising the specific outcome variables. This way we can avoid the usual approach of log transforming outcome variables, which has implications for the parallel trend assumption [32]. Log transformation would require as-random treatment allocation (not our case) or checking that the outcome distribution is not affected by the intervention itself. Log transformation also affects the interpretation depending on the model, e.g. from measuring additive to multiplicative effects [33].

Sub-Group Analysis

We will repeat our analyses of individual- and area-level outcomes for the following subgroups:

- Small versus larger SL schemes. We propose this partly because the larger schemes have been politically contentious (following the change of government in 2024, changes were announced to make it easier for LAs to set up large schemes without needing national government permission), and partly because we hypothesise that resident displacement occurs less in larger schemes particularly where the schemes extend across the whole local authority area. For this purpose, we will define larger schemes as those covering 90%+ of the Local Authority population (Census 2011): 2012_Newham, 2014_BarkingandDagenham, 2015_Croydon, 2015_Liverpool, 2015_WalthamForest. Small schemes will in this analysis be defined as those covering up to 20% of the population. Schemes of intermediate sizes will be ignored in this analysis.
- London versus outside London. Comparisons with London are useful because it has a unique housing market and some of its areas were settings for the Olympic Games (a potential confounder).

To examine impacts on equity, we will run the following area-level subgroup analyses by ranking local authorities:

- Level of deprivation: lower half (least deprived), upper half (most deprived)
- **Proportion of population from a Non-White ethnic background**: lower half (low proportion), upper half (high proportion)
- Proportion of population under 16: lower half (low proportion), upper half (high proportion)
- **Proportion of population over 75**: lower half (low proportion), upper half (high proportion)

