APS includes items that are relevant to the following equity dimensions covered in the PROGRESS+ framework: Place of residence (which we operationalise as region); Ethnicity, Occupation, Gender, Religion, Education as well as participants who live on their own and participants with child dependents. Occupational status and education can be considered proxies for socio-economic status. Furthermore, the survey asks about long term and limiting health conditions, allowing us to consider these dimensions of disability. It also asks about cohabiting same sex partners. We will incorporate these dimensions into the equity analysis where sample sizes allow us to do so.

To address potential multiple testing issues with the secondary analyses, will adjust the significance tests according to a Benjamini–Hochberg False Discovery Rate of 5% [35].

Software

The analyses will be carried out in Stata (version 18 or later)[36] or R.

19. Handling of missing data

Missing data does not constitute a significant issue with the listed data sources and the analyses will be conducted as complete case only.

20. Handling of withdrawals and replacements

Not applicable.

21. Outcome

Primary and secondary outcomes are described in detail in Section 14.

22. Data confidentiality statement

Quantitative analyses will only involve de-identified secondary data and be carried out on passwordprotected university servers unless otherwise specified by agreements with data providers. Agreements with data providers will be adhered to – including use of secure data environments.

23. Follow-up

The quantitative part of the study will only involve de-identified data where follow-up is not possible.

26. Quality assurance

The quantitative data have been through quality assurance at the source. We will still carry out checks of data completeness, consistency, and outliers. Any changes will be justified and documented in syntax files.

Part D: ETHICAL CONSIDERATION

27. Ethical approval

The project has gone through the ethical approval process at London School of Hygiene & Tropical Medicine (LSHTM submission number: 29809). On obtaining approval from LSHTM, we will then follow ethics requirements for each of the other collaborating universities (Liverpool, Lancaster, Greenwich, Bristol).

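### Subgroup questions are comparative, but the plan repeats the analysis within each subgroup and pre-specifies no test of the difference between subgroups

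*SAP*

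**What the plan says.** The Sub-Group Analysis text in Section 18 is the same in both documents. It has four parts.

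- **Scheme size and London.** "We will repeat our analyses of individual- and area-level outcomes for the following subgroups": small versus larger schemes, and London versus outside London. The larger schemes are "2012_Newham, 2014_BarkingandDagenham, 2015_Croydon, 2015_Liverpool, 2015_WalthamForest". Small schemes cover up to 20% of the authority's population, and intermediate schemes are left out. The plan hypothesises less displacement of residents in larger schemes. For the other split it says "Comparisons with London are useful because it has a unique housing market", and it names the Olympic Games as a potential confounder.
- **Area-level equity.** "To examine impacts on equity, we will run the following area-level subgroup analyses by ranking local authorities". Authorities are split into lower and upper halves on deprivation, non-White population, population under 16 and population over 75.
- **Individual-level equity.** After listing the APS items on PROGRESS+ dimensions: "We will incorporate these dimensions into the equity analysis where sample sizes allow us to do so". No method follows.
- **Multiplicity.** "To address potential multiple testing issues with the secondary analyses" (Protocol), the analysts "will adjust the significance tests according to a Benjamini–Hochberg False Discovery Rate of 5"% (SAP). The tests that make up the family are not listed.

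The only other statement on heterogeneity is in Section 9a. Different aggregation schemes for the Callaway and Sant'Anna estimator will be used to "explore the overall effect as well as treatment effect heterogeneity over time and across groups".

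**The concern.** Each of these splits asks whether the effect differs: by scheme size, by region, or between more and less deprived authorities. Assessing impacts on equity is part of the WP1 objective (Section 8b). Two separate estimates, each with its own p-value, do not answer that. One can be significant and the other not when the true effects are equal, and both can be significant when the effects differ. Neither document gives an interaction term, a difference between subgroup ATTs with an interval, a heterogeneity test, or a rule for interpreting one subgroup against another. The gap leaves room to report that licensing works in one kind of place and not in another on evidence that does not show it. The plan itself calls larger schemes politically contentious, so such a statement could carry weight.

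**Working it through.** **1. Is a test of the difference specified anywhere?** The Section 9a sentence concerns aggregating group-time effects. Groups there are cohorts defined by year of first treatment, not the subgroups of Section 18, and the stated aim is to explore. The FDR sentence adjusts tests but does not say that any of them is a test of a difference. The contrast is not specified.

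**2. Generic size.** Suppose both subgroups have the same true effect, the same power p, and independent estimates. Then P(exactly one significant) = 2p(1−p).

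- p = 0.8: 2 × 0.8 × 0.2 = 32%
- p = 0.5: 2 × 0.5 × 0.5 = 50%
- p = 0.3: 2 × 0.3 × 0.7 = 42%

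These powers are illustrative and come from neither document.

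**3. Reproducing the plan's own figure.** Section 11 states a minimum detectable difference of 25% SD for 1,635 treated LSOAs. The design is a two-period DiD with SD 1, three controls per treated unit and α = 0.05, taken as two-sided. For n treated units, SE = √[2(1/n + 1/(3n))].

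- With N as treated units, as Table 1 is labelled, N = 1,000 at 10% SD gives power 0.491. The table prints 0.167.
- With N as total units (n = N/4), the same cell gives 0.162, and 57 of 65 checked cells agree within 2 percentage points. N = 1,635 then gives 0.70 at 20% SD and 0.87 at 25% SD, so 25% SD is reproduced on the table's grid.

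Both readings are carried forward. *As printed* means n = N/4, which is what the plan's look-up of 1,635 implies. *As labelled* means n = N. This ambiguity should be cleared up in its own right.

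**4. London versus outside London.** Table 3 gives 930 treated LSOAs in London, so 1,635 − 930 = 705 lie outside. With equal true effects, P(exactly one significant) = p₁(1−p₂) + p₂(1−p₁).

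As printed, SE is 0.107 in London and 0.123 outside. At 0.25 SD the powers are 0.65 and 0.53, so 0.65 × 0.47 + 0.53 × 0.35 = 49%.

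| True effect in both (SD) | As printed | As labelled |
|---|---|---|
| 0.10 | 24% | 49% |
| 0.15 | 39% | 39% |
| 0.20 | 49% | 13% |
| 0.25 | 49% | 2% |

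**5. Other splits.** Table S1 gives 155 + 110 + 220 + 298 + 144 = 927 LSOAs in the larger schemes, of which 927 − 298 = 629 are in London. At most 1,635 − 927 = 708 are in small schemes, because intermediate schemes are dropped. Equal halves of 817 and 818 are assumed for the equity splits; ranking authorities need not divide LSOAs evenly. Discordance at 0.25 SD as printed is 49% for scheme size and 48% for the halves.

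**6. What a direct test could detect.** For London versus outside, SE of the difference = √(0.107² + 0.123²) = 0.163 as printed. With 80% power, 2.80 × 0.163 = 0.46 SD; as labelled, 0.23 SD. Power for a true difference of 0.25 SD is 34% as printed and 87% as labelled. On the 100%-coverage LSOAs (860 in London, 341 + 155 = 496 outside) the difference needed is 0.52 SD as printed and 0.26 SD as labelled.

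**7. Are the two estimates independent?** Controls are matched 1:3 with replacement within super-region. London's 2,790 control places are filled by 1,271 distinct LSOAs, so each is used 2,790/1,271 = 2.2 times on average. One control can therefore serve both sides of an equity or scheme-size split. Only London versus outside is protected, because matching never crosses that boundary. The figures for the other splits are rough for that reason, and all of them ignore clustering by authority or scheme.

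**The case against.** The text supports less than a reader might infer from it, in four ways.

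- **That each subgroup will be tested against zero, and that the FDR correction covers the wrong family.** Testing against zero is the natural reading of repeating the analyses and adjusting the significance tests, but it is not stated. The family is undefined, so it cannot be called wrong.
- **That unequal significance will be read as unequal impact.** The documents give no rule of interpretation. They leave that reading open and do not announce it.
- **That the whole equity objective rests on repeated analyses.** Repetition or subgroup analysis is stated for scheme size, London and the four area-level splits. The APS method is open and could include interactions. WP2 also assesses equity qualitatively.
- **That subgroup estimates only serve a comparison.** With the Olympics as a possible confounder, and the earlier London study's mental health index (SAMHI) result driven by one scheme (Section 7b), whether an effect exists outside London is a robustness question. The outside-London ATT answers it directly.

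It is also fair to say that these are secondary analyses, already reduced on the steering committee's advice, that the percentages depend on an unresolved reading of Table 1, and that a direct test may often be inconclusive.

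All of this limits the point, but the gap remains. The contrasts posed are not tested under the plan as written. Low power is itself a reason to show the interval for the difference, which would make the imprecision visible.

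**Conclusion.** The point holds as a missing pre-specified contrast for scheme size, London versus outside London and the four area-level equity splits. For the APS dimensions the method is simply unspecified. The risk of discordant significance under equal effects is material: about 49% for London versus outside at 0.25 SD on Table 1 as printed; as labelled, 2% at 0.25 SD, rising to 49% at 0.10 SD. It is small only where both subgroups are well powered. The calculation assumes a two-period DiD, independent estimates, two-sided 0.05, no clustering and no FDR adjustment. FDR adjustment would change the percentages, but it does not turn two separate tests into a test of their difference. The change should be made before outcome analysis; it concerns secondary analyses and leaves the primary result untouched.

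**What to change.** Add to Section 18 of the SAP, and mirror in the Protocol:

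- For each contrast, the result that answers the comparative question is the difference between the two subgroup ATTs, with a 95% CI and p-value. State the scale (additive or multiplicative), since non-linear models are planned, and use the same estimator in both subgroups.
- List the tests in the FDR family and include these difference tests.
- Take the SE by default from a joint bootstrap that resamples local authorities and re-estimates both subgroups on each resample, so that shared controls enter the covariance. The formula √(SE₁² + SE₂²) is acceptable only for London versus outside.
- Keep reporting each subgroup ATT with its CI, with the outside-London estimate as a robustness result. State that no difference will be inferred from one subgroup being significant and the other not.
- State how the APS dimensions will be analysed, on the same principle.

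**Cost.** A short SAP amendment, bootstrap computing time and some extra APS output for disclosure checks; no new data. The price is candour about precision. Before clustering, London versus outside needs a difference of about 0.46 SD for 80% power on Table 1 as printed, or 0.23 SD as labelled. Cluster inference with only five larger schemes is fragile, and since four of them are in London the size and London contrasts overlap. The report should say so.

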#### **Importance**

Housing is a social determinant of health [11]. Poor quality homes present numerous environmental risks to residents' health, including risks of injury, physical illnesses linked to cold, damp, and indoor air pollution, and risks to mental health and wellbeing [12]. As stated earlier, the cost to the NHS is high. The unequal distribution of poor-quality homes correlates with other social inequalities in health [13].

Housing improvement interventions have been shown to benefit residents' health, including mental health and wellbeing, and respiratory health and injury rates particularly when targeted at those most in need [12,14–17]. Strategies and recommendations for promoting health equity often include housing improvement [11,18].

While simple(ish) mechanisms for improving tenants' health can be hypothesised (housing improvement and greater scrutiny of landlords), SL is intended to improve area-level outcomes for the wider community [19,20]. SL is not just about refurbishment. It is also about connecting landlords more with local government regulators and addressing what government perceives to be a contributor to area decline and anti-social behaviour. SL was justified by national government as a means of tackling "unprofessional landlords," who "show no interest in managing their properties properly, often letting to anti-social tenants who cause a range of problems. This, in turn, can create misery for the local community and cause further destabilisation of these areas" [19,20]. The most recent SL guidance states, SL "can contribute to an improvement in the well-being of the occupants and wider community" [21].

Interventions such as SL that attempt to identify landlords and strengthen landlords' connection with local government regulators could potentially help address systemic problems with the PRS. They might also face barriers linked to a pre-existing culture of non-compliance amongst landlords exacerbated by (in some cases) a lack of resource, poor knowledge of the regulatory environment and at times even a failure to self-identify as landlords running an important service-sector business with legal obligations [8,22].

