We therefore use as our controls individuals who live in private rented housing in LSOAs without SL that are not direct neighbours of LSOAs with SL. From among these controls, we choose those individuals who live in LSOAs that we have matched to the treated LSOAs using characteristics of the LSOAs such as proportion of individuals who are under 16, proportion of individuals who are non-white and proportion of households classed as overcrowded.

Our individual-level outcome measures come from repeated cross-sectional data, so each year different individuals are being observed in each LSOA. The starting point for our analysis is the canonical two-way fixed effects regression specification:

$$Y_{iat} = \alpha_a + \varphi_t + \beta D_{at} + \varepsilon_{iat}$$

 Y_{iat} indicates one of our outcome measures for individual *i* in LSOA *a* in year *t*. α_a is an LSOA effect, which accounts for time-invariant differences between the LSOAs, and φ_t is a year effect, which accounts for changes over time happening in all LSOAs. D_{at} takes the value 1 if LSOA *a* is subject to an SL scheme in year *t* and 0 otherwise. β is the treatment effect, i.e. it captures the impact of the SL scheme. In the special case of only two years *t* (before and after the intervention) the ordinary least squares (OLS) estimate $\hat{\beta}$ is equivalent to the difference-in-differences estimate $\hat{\gamma}$:

$$\hat{\gamma} = \left(\bar{Y}_{SL,AFTER} - \bar{Y}_{SL,BEFORE}\right) - \left(\bar{Y}_{COMPARATOR,AFTER} - \bar{Y}_{COMPARATOR,BEFORE}\right)$$

 $\overline{Y}_{SL,AFTER}$ is the mean of the outcome measure in the LSOAs with an SL scheme after implementation of the SL scheme and $\overline{Y}_{SL,BEFORE}$ is the mean before implementation. $\overline{Y}_{COMPARATOR,AFTER}$ is the mean of the outcome measure in the matched comparator LSOAs in the year after SL was implemented in the SL areas and $\overline{Y}_{COMPARATOR,BEFORE}$ is the mean in the year before implementation. Unfortunately, this intuitive causal interpretation of the parameter estimate $\hat{\beta}$ is unlikely to apply in the more general case of more than two years *t* and the intervention being rolled out over several years. As the implementation of SL schemes is at the discretion of local authorities, they have been rolled out at different times over many years.

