13. Participant selection

The impact evaluation (WP1,3) is based on secondary data analysis and does not involve recruitment of participants.

14. Variables and data sources

14a. Variables

Individual-Level Outcomes

We have chosen outcome measures based on previous research on housing interventions and policy aims. Poor quality homes and unsafe neighbourhoods present both mental and physical risks. Our primary outcome will be **high levels of anxiety self-reported in the Annual Population Survey (APS)**, measured as people reporting a score of more than 6 in response to the question "Overall, how anxious did you feel yesterday?", where 0 is `not at all anxious' and 10 is `completely anxious'. A threshold of more than 6 on the 11-point scale has been identified by the ONS as a measure of high anxiety levels.

Our secondary outcomes will be the **three other measures of subjective wellbeing (happiness, life satisfaction and feeling worthwhile)** included in the APS. We will also examine **the general self-reported health measure collected by the APS** as an indicator of health that includes both mental and physical health. To investigate potential unintended consequences of SL, we will also examine the **APS respondent's number of years at the current address** as an indicator of residential stability.

Area-Level Outcomes

Our primary area-level outcome will be the **Small Area Mental Health Index (SAMHI)** and its individual domain scores. The index is available for LSOAs on an annual basis [13]. It combines the following measures of mental healthcare use into a single index: mental health-related hospital admissions, antidepressant treatment days per population, proportion of the population diagnosed with depression, proportion of population in receipt of mental health-related benefits.

We will complement the analysis with an exploration of physical health outcomes. Since the treated areas are relatively small, most physical health outcomes are not available at the spatial granularity needed for the analysis. However, we can use **1. All-cause emergency hospital admissions** as an

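### The APS limiting-illness strata can change make-up because of licensing, so anxiety effects estimated within them need to be read as descriptive

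*SAP*

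**What the plan says.** SAP Section 18, Sub-Group Analysis, lists APS items that map to equity dimensions; Protocol Section 18 has the same text. The list covers region, ethnicity, occupation, gender, religion and education, "participants who live on their own and participants with child dependents", same-sex cohabitation, and disability. On disability it says: "Furthermore, the survey asks about long term and limiting health conditions, allowing us to consider these dimensions of disability". The commitment carries one condition: "We will incorporate these dimensions into the equity analysis where sample sizes allow us to do so". Nothing is said about when a trait must have been measured.

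SAP Section 9a describes the data: "Our individual-level outcome measures come from repeated cross-sectional data, so each year different individuals are being observed in each LSOA".

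Three other places bear on whether licensing could change stratum membership:

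- SAP Section 14a makes general self-reported health a secondary outcome, "as an indicator of health that includes both mental and physical health".
- Protocol Section 7a (Importance) says that housing improvement has been shown to benefit health, "including mental health and wellbeing, and respiratory health and injury rates particularly when targeted at those most in need".
- Protocol Section 7c sets out hypotheses on discrimination, landlords leaving the market and polarisation. SAP Section 18 adds, on scheme size, "we hypothesise that resident displacement occurs less in larger schemes".

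**The concern.** A within-stratum DiD compares the same kind of person before and after only if licensing does not alter who falls in the stratum. Limiting illness is close to an outcome the plan expects licensing to improve. If it does improve, some treated-area tenants who would have reported a limiting condition will no longer do so. If they are less anxious than those who remain, the limiting-illness stratum looks worse after licensing although nobody's anxiety has changed. If they are more anxious than the people they join, the other stratum looks worse too.

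What is at stake is the disability part of the equity objective. No planned safeguard would reveal the problem. The Benjamini-Hochberg adjustment deals with chance findings, not with a shift in composition. The plan is careful about timing elsewhere: matching variables are taken from before the intervention or as near to it as the data permit (SAP Section 14a), and area-level equity groups rest on local-authority rankings rather than on respondents' own answers.

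**Working it through.** The plan gives no figure on this point to reproduce. The calculation below is an illustration.

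**Inputs**

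- From SAP Section 11: about 8,000 treated respondents over 2012 to 2019, and three controls per treated respondent.
- Assumed, since the documents give none: share with limiting illness s = 0.25; high anxiety pL = 0.35 with limiting illness and pN = 0.17 without; share of all respondents who leave the limiting stratum because of licensing k = 0.02 to 0.05; high anxiety among the movers pM = 0.28; half of respondents interviewed before licensing.
- The true effect on anxiety is zero for everyone. Control areas do not change, so the apparent DiD is the change in treated areas.

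**Formulas**

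- Limiting stratum afterwards: (s·pL − k·pM)/(s − k).
- Other stratum afterwards: ((1 − s)·pN + k·pM)/((1 − s) + k).

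**k = 0.02**

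- Limiting: (0.0875 − 0.0056)/0.23 = 0.0819/0.23 = 0.3561, apparent change +0.61 points.
- Other: (0.1275 + 0.0056)/0.77 = 0.1331/0.77 = 0.1729, apparent change +0.29 points.
- False contrast: 0.61 − 0.29 = about 0.3 points.

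**k = 0.05**

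- Limiting: (0.0875 − 0.0140)/0.20 = 0.0735/0.20 = 0.3675, apparent change +1.75 points.
- Other: (0.1275 + 0.0140)/0.80 = 0.1415/0.80 = 0.1769, apparent change +0.69 points.
- False contrast: 1.75 − 0.69 = about 1.1 points.

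The overall rate stays at 0.25 × 0.35 + 0.75 × 0.17 = 0.215 in both cases.

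**Sampling error of the contrast** (independent observations)

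With n treated respondents per period in a stratum, the DiD variance is 2p(1 − p)(1/n + 1/(3n)).

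- Limiting: n = 8,000 × 0.25/2 = 1,000; variance = 2 × 0.35 × 0.65 × 4/3,000 = 0.000607; standard error 2.46 points.
- Other: n = 8,000 × 0.75/2 = 3,000; variance = 2 × 0.17 × 0.83 × 4/9,000 = 0.000125; standard error 1.12 points.
- Contrast: √(0.000607 + 0.000125) = 0.0271, about 2.7 points, before any allowance for clustering.

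**Other assumptions**

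Let s be 15% or 25%, the anxiety rates 35%/15% or 40%/17%, 2 to 10% of the limiting stratum leave, and movers' anxiety equal the other stratum's or lie midway.

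- The false contrast then runs from 0.14 to 2.56 points.
- The top of the range is 40%/17% with 10% leaving at 17%: (0.40 − 0.10 × 0.17)/0.90 = 0.4256, or +2.56 points, with no change in the other stratum.
- At s = 25% the matching standard error is √(2 × 0.40 × 0.60 × 4/3,000 + 0.000125) = 0.0277, or 2.8 points. Even there the bias is about the size of the sampling error.

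**The case against.** The case on the other side has several parts.

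- **The plan fixes no model.** It says the dimensions will be incorporated, not that respondents will be split. That is so, but the text stands under the subgroup heading, and an interaction term would meet the same difficulty.
- **Not everyone is classified after licensing.** Treated respondents interviewed before licensing and all matched controls are unaffected. This stands. The fault is a possible difference in make-up between periods within treated areas.
- **The movement assumed is large.** Two to five points out of 25 means that 8 to 20% of those with limiting illness lose that status. Protocol Section 7b reports that impacts in the London study began in years 3 to 4. By Table S1, 423 of 1,635 treated LSOAs (26%) belong to schemes that started in 2018 or 2019. Movement towards the upper end is doubtful, and this keeps the point small.
- **No pre-licensing record can exist in these data**, and disability is too central to an equity analysis to drop. This also stands, and is why the dimension should be kept and its interpretation changed.

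A reader might go further in three ways that the documents do not support:

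- *That licensing also moves people between strata of occupation, living alone, dependent children or cohabitation.* The documents give no route by which a licence changes these in a person. They do give a route through tenant mix (displacement, discrimination, landlords leaving), and that reaches every stratum, including sex, ethnicity, religion and education. Confining effect claims to fixed traits would therefore give false reassurance.
- *That the disability finding would have the wrong sign.* That needs a true contrast smaller than the bias, which in the worked case lies well inside sampling error.
- *That the primary results are compromised.* They do not condition on these strata.

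**Conclusion.** The point holds for limiting illness and is modest in size. The SAP uses as a stratifier a trait that its own reasoning says licensing may change, in data where the trait is read at interview, and neither document addresses this. The conclusion about mechanism rests on the documents. The size rests wholly on assumed prevalences and movement: about 0.3 to 1.1 points in the worked case and 0.1 to 2.6 across the wider range. The bias is below, or at most about equal to, the contrast's standard error. Larger samples would not reduce it, however. It affects a secondary analysis that is conditional on sample size and FDR-adjusted. For the other APS dimensions the documents support only a caution about changing tenant mix.

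**What to change.** In SAP Section 18, Sub-Group Analysis:

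1. Add limiting illness as an individual-level outcome, analysed with the same DiD as the other APS outcomes. This gives a disability result that does not depend on stable strata.
2. Label anxiety and wellbeing effects within limiting-illness strata as descriptive, to be read alongside the result in item 1.
3. For the other APS equity dimensions, including sex, ethnicity, religion and education, run the same DiD with stratum share as the outcome. Attach a caution to within-stratum effects where the share shifts.
4. Keep all the listed equity dimensions.

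No new data are needed, and SAP Part B allows justified, transparent revisions. The cost is a few extra DiD runs inside the secondary FDR family, which goes somewhat against the earlier reduction of subgroup analyses over multiple testing (SAP version history, item 8), and a weaker claim for the disability subgroup.
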